6.3.3. Changes in 12-Lead ECG

Results of ECG are to be collected before and after ProvayBlue™ treatment, including PQ interval, QRS duration, QT interval, QTc interval and overall interpretation (normal; abnormal not clinically significant; abnormal clinically significant).

Number (%) patients in each results interpretation category at each time point will be tabulated at each planned time point (Table 14.3.7.1, Table 14.3.7.2). The PQ interval, QRS duration, QT interval, and QTc interval will not be tabulated, but a data listing will be provided (Listing 16.2.14).

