16.5. EVALUATION OF SAFETY

Refer to Section 7.2.3 for the safety endpoints.

All AEs will be displayed in summary tables, by Medical Dictionary for Regulatory Activities (MedDRA) system organ class and preferred term. Other safety data (including laboratory data) data will be summarized using appropriate descriptive statistics.

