- h. Vital signs will include: Systolic (SBP) and diastolic (DBP) blood pressure (mmHg), heart rate (beats per minute [bmp]), body temperature (°C or °F), respiration rate (breaths per minute), oxygen saturation by co-oximetry.
- i. If the patient is treated prior to consent, all available pre-treatment vital sign information should be retrieved where possible;
- j. Within 1 and 2 hours after the end of each ProvayBlueTM infusion (i.e. both Dose 1, Dose 2 and any additional dose if applicable).
- k. Additional (optional) parameters (for example blood gas) will be collected based on available data from patient standard of care.
- 1. Within 1 hour after the end of ProvayBlueTM infusion.
- m. If applicable (if the metHb level is acceptable within 1 hour after the end of Dose 1 ProvayBlueTM infusion, the repeat dose of ProvayBlueTM will not be needed).
- n. If applicable, in case of administration of additional doses of ProvayBlue at the discretion of the Investigator
- o. Collection of ECG data is mandatory at admission and approximately at 24 hours after the end of the last ProvayBlue™ infusion or just prior to discharge from the clinic if earlier than 24 hours. The collection of additional data will be based on available 12-lead ECG recordings performed as per patient standard of care as appropriate to determine general condition.
- p. ProvayBlueTM will be administered IV at a dose of 1 mg/kg over 5-30 minutes. If the methemoglobin level remains greater than 30% or if clinical signs and symptoms persist, a repeat dose of 1 mg/kg may be given 1 hour after the first dose. Depending on the clinical status of the patient, additional doses may be administered at the discretion of the Investigator. The data on these additional doses will be recorded in the study CRF.
- q. PK blood samples are to be drawn at the discretion of the Investigator. The suggested schedule of PK blood sampling is:
 - Approximately 1 hour after the end of each ProvayBlueTM infusion (i.e. Dose 1, Dose 2 and any additional dose if applicable);
 - Prior to Dose 2 (or any additional dose) ProvayBlue™ infusion (if applicable);
 - Approximately 24 hours post the end of the last ProvayBlue™ infusion, or just prior to discharge from the clinic if earlier than 24 hours.
- r. Collection of concomitant medications/medical procedures from PICD signature or the start of ProvayBlueTM treatment (whichever occurs sooner) until 10 to 15 days after the last administration of ProvayBlueTM;

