2. OVERVIEW OF STUDY OBJECTIVES AND ASSESSMENTS

2.1. Study Objectives and Endpoints

An overview of study objectives and study endpoints is provided in Table 1. The Observational Study was designed to mirror the objectives, endpoints, and data collection elements of the Interventional Study, with modifications to (1) reflect the nature of observational data, where the specific timing of procedures and measurements is driven by institutional standard care, not a study protocol, and (2) to streamline the protocol and study procedures where possible.

Table 1: Overview of Study Objectives and Endpoints

Protocol Number	PVP-2016003 (Interventional Study)	HQF-METHB-2018001 (Observational Study)
Primary Objective	To confirm that ProvayBlue™ after a single administration is efficacious in patients with acquired methemoglobinemia	To confirm that ProvayBlue™ is efficacious in patients with acquired methemoglobinemia
Secondary Objectives	
 • To evaluate the efficacy of a single dose of 1 mg/kg of ProvayBlue™; • To evaluate the efficacy of a second dose of 1 mg/kg of ProvayBlue™ to further reduce metHb levels when metHb is not fully reduced by a single dose; • To evaluate the normalization of the respiratory rate, heart rate and blood pressure of patients who achieve a reduction in metHb level within 2 hours of receiving the first dose of ProvayBlue™; • To confirm the safety and tolerability of ProvayBlue™ injection in patients with acquired methemoglobinemia. 	To confirm the safety and tolerability of ProvayBlue™ in patients with acquired methemoglobinemia
Study Population	Patients who present in hospital/urgent care setting diagnosed with acquired methemoglobinemia. The population may include pediatric and adult patients (males and females of all ages are included).	Patients who are diagnosed in any care setting with acquired methemoglobinemia. The population may include pediatric and adult patients (males and females of all ages are included).

Protocol Number	PVP-2016003 (Interventional Study)	HQF-METHB-2018001 (Observational Study)
		
Primary Treated Group: At least ten (10) patients who are treated for acquired methemoglobinemia that is symptomatic (eg, exhibiting sleepiness, cyanosis, dizziness) and/or with measured methemoglobin levels $>30\%$
 
Secondary Treated Group: Up to ninety (90) additional asymptomatic patients who are treated for acquired methemoglobinemia with measured methemoglobin levels $\leq 30\%$

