3.1. Database Structure

It is the intention of Provepharm to enter selected, pertinent CRF data elements from the Interventional Study into the database serving the Observational Study for the purpose of preparing the data summary for PMR-3065-1.

It is therefore expected that certain procedures will have to take place before the CRF data elements from the Interventional Study can be entered into the electronic database. Those procedures include but are not limited to converting the absolute calendar dates from the Investigational Study CRFs to the relative study days used in the database. The integrated datasets will mimic the SDTM structure and naming convention whenever possible.

In study PVP-2016003, PK blood draws were planned and plasma concentration were to be determined. However, PK data are not collected due to poor PK blood sample handling. Therefore, the corresponding dataset (PC) will not be created.

In a situation where a data field that is planned in one protocol but not in the other protocol, the missing data will be marked as 'Not Done' in the database. For instance, the Observational - Study (HQB-METHB-2018001) collects "Patient setting before first presentation", "Diagnosed by", "Diagnosis setting". These 3 questions are not included in the Interventional Study. Hence, data value will be set to 'Not Done' in 'Patient setting before first presentation' dataset XD for patients from the Interventional Study (PVP-2016003).

Table 3: Expected SDTM Domains for the Pooled Database

Name of Data Collection Elements/Form	SDTM Domain
Demographics (age, sex, race, ethnicity)	DM
Weight and height at enrollment	VS
Patient setting before first presentation	XD
Past medical history	MH
Acquired methemoglobinemia diagnosis, including diagnosis ICD-10 Code	XD
Methemoglobinemia assessment and treatment before receiving study drug	XD
Methemoglobinemia signs and symptoms	CE
Co-oximetry before and after ProvayBlue™ treatment	LB
Arterial blood gas	LB
ProvayBlue™ administration	EX
Other treatment for methemoglobinemia	CM
Vital signs	VS
ECG	EG
Hematology, biochemistry, and other labs	LB
Medications and procedures	CM, PR
Hospital course	HO
Adverse events	AE
Follow-up overview and questionnaires	QS

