5.1.1. MetHb Level at 1-hour Post Dosing

The timing of postdosing metHb level assays is inconsistent in clinical practice and may not be obtained until hours after the conclusion of first dose infusion in the emergency department. It should be noted that, consistent with such practice, the Observational Study does not have a prespecified schedule for metHb postdosing collection. MetHb level at 1-hour postdosing will be derived using linear interpolation. This method will be referred to as backward linear interpolation if the first postdosing metHb was after 1 hour, or forward linear interpolation if the first postdosing metHb was before 1 hour. This method will be mathematically expressed as follows.

Step 1: calculate rate of metHb change per minutes)

$$= (\text{metHb_1} - \text{baseline}) / \text{time of metHb_1 in minutes}$$

Step 2:

$$\text{metHb_1hr} = \text{baseline} + 60 * [(\text{metHb_1} - \text{baseline}) / (\text{time of metHb_1 in minutes})]$$

where

- baseline = baseline metHb defined as the last metHb before the first dose of study drug)
- metHb_1 = first post treatment metHb observation
- constant (60) converted the time units from minutes to hours

For example, a patient has metHb of 74.40 at baseline and 15.70 at 70 minutes postdosing. The estimated metHb_1hr is 24.08571.

Percent change from baseline (PCHG) at 1-hour post dosing can be estimated as follows.

$$\text{PCHG (\%)} \text{ at 1-hour post dosing} = 100 * [(\text{metHb_1} - \text{baseline}) / \text{time of metHb_1 in minutes}] / \text{baseline}$$

The PCHG for the above example is -67.63%.

$$\text{PCHG at 1-hour} = 100 * \{ [60 * (15.7 - 74.4) / 70] / 74.4 \}$$

Due to the mathematical property of this derivation, a patient could never achieve 50% reduction at 1-hour post dosing if the first postdosing metHb was taken after 2 hours. Hence, this derivation will be applied only to those patients who had first postdosing metHb before 2 hours.

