5.2.3. Summaries of Vital Signs Change from Baseline

A summary table will include VS measurement and change from baseline by relative time frame with descriptive statistics of sample size, mean, standard deviation, 2-sided 95% confidence intervals, quartiles (25% tile, 50% tile [median], and 75% tile), minimum, and maximum. The table will also include number (%) patients whose vital signs are within the normal range (Table 14.2.2.1). Number (%) patients who had at least 1 incidence of normal vital signs within the 2 hours following the completion of first dose ProvayBlueTM infusion will also be presented.

Change in SpO₂ will be assessed in 3 categories, based on $\pm 2\%$ rule as follows

- 1) Increased if the difference (postbaseline – baseline) is >2
- 2) No Change if the difference (postbaseline – baseline) is within ± 2
- 3) Decreased if the difference (postbaseline – baseline) is <2

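### No planned table pairs a patient's baseline with post-dose ECG or vital-sign status so as to count those who worsened

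*SAP*

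**What the plan says.** Protocol 7.2.3 names physical examination, vital signs, hematology and biochemistry, ECG and adverse events as safety endpoints. Protocol 16.5 adds: "Other safety data (including laboratory data) data will be summarized using appropriate descriptive statistics". SAP Table 1 repeats the list for the Interventional Study but gives only adverse events as the safety assessment of the Observational Study. SAP 3.3.3 then keeps adverse events, laboratory tests and ECG as the safety endpoints to be summarized. SAP section 1 says that the SAP prevails over the protocol's statistical section.

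- **ECG (SAP 6.3.3).** "Number (%) patients in each results interpretation category at each time point will be tabulated at each planned time point". Section 7.1 plans this table for Primary cases and for all safety patients. For the measured intervals: "The PQ interval, QRS duration, QT interval, and QTc interval will not be tabulated, but a data listing will be provided". No ECG plot is planned.
- **Vital signs (SAP 5.2, Table 14.2.2.1).** The only table is on the Efficacy Analysis Set and covers baseline and the first 2 hours. It gives values and change from baseline, and on status: "The table will also include number (%) patients whose vital signs are within the normal range". It also counts patients with at least one normal reading in that window.
- **Physical examination.** It appears in SAP Table 1 but has no data domain in Table 3 and no table, figure or listing in section 7. Section 3.1 intends to "enter selected, pertinent CRF data elements from the Interventional Study into the database".

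**The concern.** Confirming safety and tolerability is an objective of both studies. The package insert in Protocol Appendix 1 asks for vital-sign and ECG monitoring during treatment. It reports one serious case of syncope due to sinus pauses, and lists tachycardia and hypertension among reactions to the product class. A reader of the safety report will want to know how many patients had an acceptable ECG or blood pressure before dosing and a worse one afterwards. The planned tables do not give that number. The ECG table shows how many were abnormal at each time, but not whether they were the same patients. The vital-sign status counts look for recovery, because the table was built for efficacy.

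**Working it through.** The plan states no figure on this point to reproduce. The check compares the planned outputs with the safety endpoints, then asks what the ECG counts can show.

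**1. Who has planned ECG times.** For the Interventional Study, Protocol Appendix 2 says "Collection of ECG data is mandatory at admission and approximately at 24 hours after the end of the last" infusion, or before discharge if that is earlier. For the Observational Study, SAP 2.1 describes a setting "where the specific timing of procedures and measurements is driven by institutional standard care, not a study protocol". SAP section 1 gives 7 and 24 enrolled patients:

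- documented planned ECG times: 7 / (7 + 24) = 7/31 = 22.6%
- none documented: 24/31 = 77.4%

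The second figure rests on inference. The one explicit statement, "the Observational Study does not have a prespecified schedule for metHb postdosing collection", concerns metHb. The registry protocol is not among the documents, and the number of registry patients with any ECG is unknown.

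**2. What separate counts can show.** Let n patients have an ECG at both times, b of them abnormal at baseline and a abnormal after dosing. The number newly abnormal lies between max(0, a − b) and min(a, n − b). With assumed counts b = 3, a = 3:

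- n = 7: from max(0, 0) = 0 to min(3, 4) = 3
- n = 31: from max(0, 0) = 0 to min(3, 28) = 3

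The table would look the same if nobody changed or if three patients worsened and three improved. If different patients have ECGs at the two times, the counts are not even comparable.

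**3. Vital signs.**

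- *Population.* The Efficacy Analysis Set (SAP 3.2) excludes Secondary cases and anyone without metHb both before and after infusion.
- *Time.* Appendix 2 schedules vital signs at 24 hours, discharge and the follow-up visit. These readings enter no vital-sign table.
- *Summary.* SAP 5.2.1 reduces the readings within 2 hours to a per-patient median, which dampens a brief extreme.
- *Direction.* SAP 5.2.2 links baseline to later status only for improvement: normalization, and time to first normal reading in patients abnormal at baseline. A patient who was normal before and abnormal after is not counted as such.
- *Exception.* SpO2 has a category for decrease, but it is written as a difference below 2. A change of −1, 0 or +1 therefore falls both there and in the no-change band of ±2, so this count is not usable as written.

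**4. Physical examination.** Nothing is planned in SAP 3.3.3, Table 3, 7.1 or 7.2.

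**The case against.** The strongest reply is that worsening is already counted, as adverse events. Protocol 15.2.1, 15.2.2 and 15.2.6 make new or worsening clinically significant examination, vital-sign and ECG findings adverse events. SAP 6.2 tabulates patients with treatment-emergent events by preferred term, severity and relationship, for Primary cases and for all safety patients. The vital-sign table gives change from baseline with minimum and maximum. Listings 16.2.9 and 16.2.14 cover every safety patient, and the report is built around narratives. With at most 31 patients, a reader can pair results by hand.

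Much of this stands, and it rules out three stronger readings that a reader might infer:

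- *That deterioration shows only in individual plots or nowhere.* It does not: the outputs just named show it, and ECG has no plot at all.
- *That syncope, tachycardia or hypertension could not be counted.* When reported, they are adverse-event terms and enter those tables. Syncope and arrhythmias are also among the prespecified signs in SAP 5.3.
- *That the ECG table fails for 77% of patients.* The documents do not show how many registry patients have ECGs. SAP 3.3.3 speaks only of ECG before and after treatment, so the reference to planned times may be loose wording.

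The adverse-event route still has limits. The rules in Protocol 15.2 cover only changes judged clinically significant after consent is signed, while dosing may come first. The general reporting period in 15.3.3.1 does reach back to the start of treatment, which softens this. No equivalent rule is shown for the registry, where SAP 2.2.1 describes largely passive chart review. Listings and narratives leave the count to the reader.

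**Conclusion.** The gap is real but limited. No planned table pairs baseline with post-dose ECG status, or counts patients whose blood pressure, heart rate or respiratory rate went from normal to abnormal. Vital signs after 2 hours, and those of Secondary cases, enter no vital-sign table. Physical examination has no planned output. Other outputs cover part of this, so what is missing is a direct count of patients who worsened, rather than all sight of worsening.

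The size cannot be fixed from the documents. Planned ECG times are documented for 7 of 31 patients. How many of the other 24 have ECGs, and how many are Secondary cases, is not stated. The 0-to-3 range is an illustration on assumed counts. The point about registry timing is inferred from a general statement in SAP 2.1. The reason for omitting physical examination is also unknown: Table 3 lists expected domains, and the Data Integration Plan is not supplied. The change is still worth making, because it is cheap and does not depend on scheduled visits.

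**What to change.** 1. **ECG.** Replace the table in SAP 6.3.3 with a shift table: baseline interpretation (normal; abnormal, not clinically significant; abnormal, clinically significant; missing) against the worst post-dose interpretation. Produce it for Primary cases and for all safety patients, and show how many have both a baseline and a post-dose ECG. At the same time align the table numbers, which are 14.3.7.1 and 14.3.7.2 in 6.3.3 but 14.3.6.1 and 14.3.6.2 in 7.1.
2. **Vital signs.** Add a safety-set shift table for SBP, DBP, heart rate and respiratory rate, from baseline to worst post-dose category (low, normal, high) through 24 hours or discharge. Classify the lowest and the highest reading separately, since one patient can go both ways, and report the number of readings per patient. Correct the SpO2 categories so that they do not overlap.
3. **Physical examination (optional).** Enter and list the findings of the 7 interventional patients. This adds little.

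The cost is a few more outputs and, for item 3, data entry from 7 paper CRFs. Two limits need footnotes. Worst-value counts rise with the number of readings, so closely monitored patients will look worse. The SAP Table 4 ranges are narrow in children, for example a heart rate of 60-70 at ages 3 to 5 and 12 to 15, and the protocol offers the same ranges only as examples, so many paediatric values will be flagged.

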7. ABLE OF CONTENTS OF PLANNED DATA SUMMARIES

7.1. Summary Tables

Number	Type	Title	Analysis Set
14.1.1	Table	Patient Enrollment and Analysis Set and Post Treatment Follow-up Status	Enrolled Analysis Set
14.1.2.1	Table	Demographics and Baseline Characteristics	Safety Analysis Set - Primary Cases
14.1.2.2	Table	Demographics and Baseline Characteristics	Safety Analysis Set - All Patients
14.1.2.3	Table	Demographics and Baseline Characteristics	Efficacy Analysis Set
14.2.1.1	Table	Predicted MetHb Level 1 Hour Post First Infusion in Patients with First MetHb Drawn Within 2 Hours of Dosing	Efficacy Analysis Set
14.2.1.2	Table	Summary of 1st Follow-up MetHb Level Regardless When the Assessment Was Taken	Efficacy Analysis Set
14.2.1.3	Figure	Individual Profile of Change from Baseline in MetHb Before and After Treatment	Safety Analysis Set - All Patients
14.2.2.1	Table	Summary of Vital Signs at Baseline and Within 2 Hours Post First Infusion	Efficacy Analysis Set
14.2.2.2	Figure	Individual Profile of Change from Baseline in Vital Signs Before and After Treatment	Safety Analysis Set - All Patients
14.2.3.1	Table	Summary of Methemoglobinemia Signs and Symptoms Before and After Treatment	Efficacy Analysis Set
14.2.3.2	Figure	Scatter Plots Showing Individual Profile of Methemoglobinemia Signs and Symptoms Before and After Treatment	Efficacy Analysis Set
14.3.1.1	Table	Study Drug Infusions	Safety Analysis Set - Primary Cases
14.3.1.2	Table	Study Drug Infusions	Safety Analysis Set - All Patients
14.3.2.1.1	Table	Topline Summary of Treatment Emergent Adverse Event	Safety Analysis Set - Primary Cases
14.3.2.1.2	Table	Topline Summary of Treatment Emergent Adverse Event	Safety Analysis Set - All Patients
14.3.2.2.1	Table	All TEAE by Preferred Term Displayed the Most Commonly Reported Event First	Safety Analysis Set - Primary Cases
14.3.2.2.2	Table	All TEAE by Preferred Term Displayed the Most Commonly Reported Event First	Safety Analysis Set - All Patients
14.3.2.3.1	Table	All TEAE by SOC and Preferred Term	Safety Analysis Set - Primary Cases
14.3.2.3.2	Table	All TEAE by SOC and Preferred Term	Safety Analysis Set - All Patients
14.3.2.4.1	Table	All TEAE by SOC, Preferred Term and Intensity	Safety Analysis Set - Primary Cases
14.3.2.4.2	Table	All TEAE by SOC, Preferred Term and Intensity	Safety Analysis Set - All Patients
14.3.2.5.1	Table	All TEAE by SOC, Preferred Term and Relationship to Study Drug	Safety Analysis Set - Primary Cases
14.3.2.5.2	Table	All TEAE by SOC, Preferred Term and Relationship to Study Drug	Safety Analysis Set - All Patients
14.3.2.6.1	Table	All Serious TEAE by SOC and Preferred Term	Safety Analysis Set - Primary Cases

14.3.2.6.2	Table	All Serious TEAE by SOC and Preferred Term	Safety Analysis Set - All Patients
14.3.3	Figure	Individual Profile of Blood Gas Results Before and After Treatment	Safety Analysis Set - All Patients
14.3.4	Figure	Individual Profile of Hematology Test Results Before and After Treatment	Safety Analysis Set - All Patients
14.3.5	Figure	Individual Profile of Biochemistry Test Results Before and After Treatment	Safety Analysis Set - All Patients
14.3.6.1	Table	Summary of 12-Lead ECG Results by Interpretation Category and Timepoint	Safety Analysis Set - Primary Cases
14.3.6.2	Table	Summary of 12-Lead ECG Results by Interpretation Category and Timepoint	Safety Analysis Set - All Patients

7.2. Data Listings

Number	Title	Analysis Set
16.2.1	Disposition and Analysis Population	ITT Analysis Set
16.2.2	Demographics	Safety Analysis Set - All Patients
16.2.3	Medical History	Safety Analysis Set - All Patients
16.2.4	Methemoglobinemia Assessment and Diagnosis	Safety Analysis Set - All Patients
16.2.5	Study Drug Administration	Safety Analysis Set - All Patients
16.2.6	Prior and Concomitant Medications	Safety Analysis Set - All Patients
16.2.7	Other Procedures During Study	Safety Analysis Set - All Patients
16.2.8	MetHb Derived Efficacy Parameters	Safety Analysis Set - All Patients
16.2.9	Vital Signs and Change from Baseline	Safety Analysis Set - All Patients
16.2.10	All Adverse Events Reported in the Study	Safety Analysis Set - All Patients
16.2.11.1	Study Identified Hematology Test Results	Safety Analysis Set - All Patients
16.2.11.2	Study Identified Biochemistry Test Results	Safety Analysis Set - All Patients
16.2.11.3	Results from Other Lab Tests Collected	Safety Analysis Set - All Patients
16.2.12	Blood Gas Parameters Results	Safety Analysis Set - All Patients
16.2.13	Methemoglobinemia Signs and Symptoms	Safety Analysis Set - All Patients
16.2.14	12-Lead ECG Results	Safety Analysis Set - All Patients
16.2.15	Follow-up	Safety Analysis Set - All Patients
16.2.16	Listing of Hospital Course	Safety Analysis Set - All Patients
